# 5.2 Derivations of Safety Endpoints

Baseline definition for all safety endpoints is given in Section 5.3. Change from baseline is calculated as on-treatment value minus the baseline value. Handling of time points is described in Section 5.4.

Treatment-emergent Adverse Event

An AE is a treatment-emergent AE (TEAE) if the AE start date is

- on or after the date of the first dose of investigational product (IP) and no later than 28 days after the last dose of IP for subjects who have completed the study or have discontinued early by the time of database cut, or
- on or after the date of the first dose of IP for subjects who are ongoing at the time of database cut

Protocol Number: 20200058

Date: 07 February 2023

Page 31 of 67

If the treatment-emergent status of an AE is unclear due to a missing/incomplete start date, it will always be considered treatment-emergent, unless shown otherwise by data. Date imputation rules for partially missing AE start dates are described in Section 8.3.1

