- For all other subjects (i.e., subjects who discontinue prior to Week 16/Visit 5), the date of the last study visit (including the Early Termination Visit and the Observational Follow-up Visit; i.e., all data after the start date will be included) for efficacy analyses, or 28 days after the last dose of IP or the date of death (if applicable), whichever comes first, for safety analyses.

For the Placebo-controlled Phases, the start date is exclusive, and the stop date is inclusive for efficacy analyses, and safety analyses of laboratory, vital signs, weight, and ECG data. For AE analyses, the start date is inclusive, the stop date under the first 2 bullets is exclusive and the stop date under the third bullet is inclusive.

- Apremilast-exposure Period:
  - Start date:
    - The date of the first dose of apremilast after being randomized (at Week 0/Visit 2) or escaped/transitioned (at Week 16/Visit 5 or Week 24/Visit 6) to an apremilast dose group.
  - Stop date:
    - For efficacy analyses, the date of the last study visit available in the database (including the Early Termination Visit and the Observational Follow-up Visit; i.e., all data after the start date of the Apremilast-exposure Period will be included), or
    - For safety analyses, 28 days after the last dose of apremilast or the date of death (if applicable), whichever comes first, for subjects who have completed the study or have discontinued early by the time of database cut. For ongoing subjects, the data cutoff

Protocol Number: 20200058
Date: 07 February 2023
Page 34 of 67

date for safety analyses of laboratory, vital signs, weight, and ECG data, and AE analyses.

For the Apremilast-exposure Period, the start date is exclusive and the stop date is inclusive for efficacy analyses, and safety analyses of laboratory, vital signs, weight, and ECG data. For AE analyses, both the start and stop dates are inclusive.

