#### 9.6 Safety Analyses

#### 9.6.1 Analyses of Primary Safety Endpoint

Safety will be evaluated via descriptive statistics and point estimates. Unless otherwise specified, all safety analyses described in this section will be performed for both the Placebo-controlled and Apremilast-exposure Phases (Section 5.5).

Safety analyses for the Placebo-controlled Phase will be based on the safety population and presented by treatment group (apremilast 30 mg BID and placebo); the data included are up to Week 16/Visit 5 for placebo-treated subjects who early escape and up to Week 24/Visit 6 for all other subjects. For the Apremilast-exposure Period, the analyses will be based on the apremilast subjects as treated population and include data from Day 1 of apremilast exposure, irrespective of when the apremilast exposure starts (at Week 0, 16, or 24). For both the Placebo-controlled Phase and the Apremilast-exposure Period, the data included will be up to 28 days after the last dose of IP or the date of death (if applicable), whichever comes first, for subjects who discontinue prematurely.

For the analyses of AEs and marked abnormalities, the following point estimates are provided, unless otherwise specified:

 Subject incidence: Subject incidence (i.e., percentage [%] used in a frequency summary) is defined as the number of subjects with the specific event divided by the number of subjects included in the analysis, multiplied by 100. Subjects with multiple occurrences of a specific event in a defined exposure interval will be counted only once in the numerator.

Protocol Number: 20200058

Date: 07 February 2023

Page 55 of 67

• Exposure-adjusted incidence rate (EAIR) per 100 subject-years: The EAIR per 100 subject-years is defined as 100 times the number of subjects with the specific event divided by the total exposure time (in years) among subjects included in the analysis. Subjects with multiple occurrences of the specific event in a defined exposure interval will be counted only once in the numerator. The EAIR per 100 subject-years is interpreted as the expected number of subjects with at least one occurrence of the specific event per 100 subject-years of exposure to the IP.

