Total exposure time: The total exposure time in years is calculated by dividing the sum of exposure time in days over all subjects included in the analysis by 365.25 days. The exposure time for a subject without the specific event is the treatment duration, whereas the exposure time for a subject with the specific event is the treatment duration up to the start date (inclusive) of the first occurrence of the specific event. If the subject experiences an event which starts on the first dose of the phase/period, the exposure time of that subject for that event is 1 day.

In summaries of continuous variables with summary statistics by time point, values for baseline, time point, and change from baseline will be summarized at each time point for subjects who have values at both baseline and the specific post-baseline time point. Frequency summaries of shifts from baseline to post-baseline time points will be provided for subjects who have values at both baseline and each individual specific post-baseline time point. In addition to the scheduled visits, shift summaries will also be provided from baseline to the end of phase/period and to the worst value, including scheduled and unscheduled visits, in a specific post-baseline phase/period.

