#### 9.6.9 Exposure to Investigational Product

Descriptive statistics will be produced to describe the exposure to investigational product by treatment group. Compliance to each IP will also be summarized.

Page 59 of 67

Protocol Number: 20200058 Date: 07 February 2023

Treatment duration will be summarized by treatment group for the Placebo-controlled Phase using the safety population.

Summary statistics for treatment duration (in weeks), as well as a frequency summary of treatment duration categories (e.g., < 4,  $\ge 4$  - < 8 weeks, etc.) and exposure categories (e.g.,  $\ge 1$  day,  $\ge 4$ ,  $\ge 8$  weeks, etc.), will be provided.

Treatment duration (in weeks) is calculated as (the date of the last dose of IP – the date of the first dose of IP + 1) / 7 and rounded to one decimal place.

When partially missing last dose date is available, set last dose date to the maximum of [the earliest possible date given the non-missing field(s) of last dose date, the minimum of (the latest possible date given the non-missing field(s) of last dose date, last known date in database, first non-missing Early Termination (ET) visit date)].

When the last dose date is completely missing, set the last dose date to the minimum of (the last known date in database, first non-missing Early Termination (ET) visit date).

Last known date in database is defined as maximum of (last visit date, clinical efficacy assessment date, lab, vital signs, AE start or end dates, concomitant medications start or end dates, concomitant procedure date, treatment exposure start date or end date where doses were completely or partially taken, death date).

The specific definitions of the first and last dose dates for the Placebo-controlled Phase and Apremilast-exposure Period are given below:

- Placebo-controlled Phase:
  - First dose date: The date of the first dose of IP.
  - Last dose date:
    - the date prior to Week 16/Visit 5 for placebo-treated subjects who escape early at Week 16/Visit 5 and take at least one dose of IP dispensed at that visit, or
    - the date prior to Week 24/Visit 6 for subjects who complete Week 24/Visit
       6 dose, except for placebo-treated subjects who escape early
    - For all other subjects (i.e., subjects who discontinue prior to Week 24/Visit 6), the date of the last dose of IP in the study.

Page 60 of 67

Protocol Number: 20200058 Date: 07 February 2023

e: 07 February 2023 Page 61 of 67

- Apremilast-exposure Period:
  - First dose date:

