    - The date of the first dose of apremilast after being randomized (at Week 0/Visit 2) or transitioned (at Week 16/Visit 5 or Week 24/Visit 6) to apremilast.
  - Last dose date:
    - The date of the last dose of apremilast.

The treatment compliance (in %) for each subject will be computed as 100 times the total number of tablets taken (the total number of tablets dispensed minus the total number of tablets returned) over the analysis phase or period divided by the intended total number of tablets that should have been taken over the same phase or period.

Summary statistics for compliance (%) will be provided by treatment arm for each analysis phase or period. Frequency summary tables of compliance will also be presented with the following categories: < 75%,  $\ge 75\%$  -  $\le 120\%$ , and > 120%.

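### The adverse-event EAIR counts events up to 28 days after the last dose but divides by time ending at the last dose, so it overstates the rate when events start in that tail

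*SAP*

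**What the plan says.** SAP 9.6.1 defines the EAIR as "100 times the number of subjects with the specific event divided by the total exposure time (in years) among subjects included in the analysis". It interprets the result as the expected number of subjects with at least one event per 100 subject-years on investigational product.

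**Denominator.** SAP 9.6.1: "The exposure time for a subject without the specific event is the treatment duration". For a subject with the event, duration is counted up to the event's start. SAP 9.6.9 computes treatment duration as last dose date minus first dose date plus one day. For the Apremilast-exposure Period the end point is "The date of the last dose of apremilast".

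**Numerator.** SAP 5.2 treats an adverse event as treatment-emergent if it starts "no later than 28 days after the last dose of IP for subjects who have completed the study or have discontinued early". SAP 5.5 closes the Apremilast-exposure Period accordingly: "For safety analyses, 28 days after the last dose of apremilast or the date of death (if applicable), whichever comes first". That stop applies to subjects who have completed or discontinued; ongoing subjects stop at the data cutoff. In the Placebo-controlled Phase, SAP 5.5 gives the 28-day tail only to subjects who discontinue. Week 24 completers stop at their first Week 24 dose, and placebo early escapers at their first Week 16 dose.

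**A third statement.** SAP 9.6.1, describing the data included for both phases, mentions the 28-day limit only for subjects who discontinue prematurely.

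**The concern.** No section adds the 28 days to the exposure time. Events in the tail enter the numerator while the days on which they could occur are left out of the denominator, so the ratio is not the rate that SAP 9.6.1 says it is. The error can only be upward. The tail is actively observed: Protocol 6.3.1, 6.5.8 and 10.1 require adverse events to be collected for 28 days after the last dose.

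Under SAP 5.5 the mismatch also differs between phases. Phase completers in the Placebo-controlled Phase are essentially aligned, because their events stop at the next-phase dose and SAP 9.6.9 sets their last dose to the day before that visit. In the Apremilast-exposure Period, completers carry the tail too. At stake is the descriptive reading of long-term adverse-event rates, which Protocol 9.7 wants adjusted for exposure and which SAP 7.3 makes part of the final analysis.

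**Working it through.** The plan states no EAIR value, so there is no figure to reproduce. The check applies the SAP's definition.

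**Inputs from the documents.** Full apremilast treatment is 48 weeks (336 days). A switch at Week 16 leaves 32 weeks (224 days), and a switch at Week 24 leaves 24 weeks (168 days). The tail is 28 days and allocation is 2:1. Dropout is 15% over the Placebo-controlled Phase (Protocol 9.3; SAP 3.2 ties the same 15% to the primary endpoint).

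**Assumptions not in the documents.** Dropout is uniform within each phase. Extension dropout is 10% (range 5% to 20%). Early escape occurs in 30% of placebo subjects who do not drop out (range 0% to 50%). The on-treatment hazard L is constant, and the tail hazard is f × L.

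**Formula.** For on-treatment time T and tail t:

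- expected subjects with an event = 1 − exp(−LT) + exp(−LT) × [1 − exp(−fLt)]
- SAP exposure time = [1 − exp(−LT)] / L
- inflation = (sum of events) / (L × sum of exposure) − 1

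For rare events this tends to f × (sum of t) / (sum of T).

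**By treatment path, f = 1, rare events.** 28/336 = 8.3%; 28/224 = 12.5%; 28/168 = 16.7%.

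**Placebo-controlled Phase, f = 1, rare events.**

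- 15% dropout: (0.15 × 28) / (0.85 × 168 + 0.15 × 84) = 4.2/155.4 = 2.7%
- 5% dropout: 1.4/163.8 = 0.9%; 25% dropout: 7/147 = 4.8%
- placebo arm, 15% dropout and 30% early escape: 4.2 / [0.85 × (0.7 × 168 + 0.3 × 112) + 12.6] = 4.2/141.1 = 3.0%
- unequal dropout: 10% gives 2.8/159.6 = 1.8%; 20% gives 5.6/151.2 = 3.7%

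**Apremilast-exposure Period at the final analysis, SAP 5.5 window.**

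| Group | Share of randomized | Mean days on apremilast |
|---|---|---|
| Apremilast, stops before Week 24 | 0.1000 | 84 |
| Apremilast, stops in extension | 0.0567 | 252 |
| Apremilast, completes | 0.5100 | 336 |
| Week 24 switch, stops early | 0.0198 | 84 |
| Week 24 switch, completes | 0.1785 | 168 |
| Week 16 switch, stops early | 0.0085 | 112 |
| Week 16 switch, completes | 0.0765 | 224 |

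The shares sum to 0.95; the other 0.05 are placebo dropouts who never take apremilast. The products sum to 243.8 days, a mean of 243.8/0.95 = 256.6 days (36.7 weeks). Inflation is 28/256.6 = 10.9% in the rare-event limit and 10.8% at L = 0.02 per year. Over the assumed dropout and escape ranges it stays between about 10% and 12%.

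**Sensitivity (Placebo-controlled, then Apremilast-exposure).** Tail hazard half the on-treatment hazard, rare events: 1.4% and 5.4%. Very common event, L = 1.5 per year, f = 1: 2.5% and 6.7%. No events in the tail: 0% and 0%.

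**If the tail applies only to premature discontinuers.** Their share is 0.1000 + 0.0567 + 0.0198 + 0.0085 = 0.185. Inflation in the Apremilast-exposure Period becomes 0.185 × 28 / 243.8 = 2.1%, close to the 2.7% of the Placebo-controlled Phase.

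**Matched windows.** Under a constant hazard, putting both parts on one window gives a ratio of 1.000 to the true hazard in both phases.

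**The case against.** The strongest reply is that this changes no conclusion. Safety is descriptive, no test or decision uses the EAIR, and the SAP plans no comparison of EAIRs between phases. Subject incidence does not use this denominator, and SAP 9.6.2 tabulates new events by exposure interval, which is the better tool for time trends. All of that stands and keeps the point minor.

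The tail hazard is also probably lower than assumed for the best-known events. Protocol 6.5.5 places most diarrhea in the first two weeks, and Protocol 1.2.1.2 reports gastrointestinal events falling with longer exposure. This stands too, so the percentages are upper bounds.

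The wording of SAP 9.6.1 is the most serious objection to the inequality between phases. If only premature discontinuers carry a tail, that inequality largely disappears. Against this, SAP 9.6.1 refers to Section 5.5 for the phases, and SAP 5.2 and 5.5 expressly include completers. The conflict is unresolved in the text.

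Three stronger readings are tempting but unsupported:

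- A reader might infer that every subject in the Apremilast-exposure Period adds 28 uncounted days. SAP 5.5 stops ongoing subjects at the data cutoff and truncates at death, so ongoing subjects have no tail at the Week 24 analysis.
- A reader might infer that the randomized safety comparison is materially biased. Only discontinuers carry a tail there, and at equal dropout the arms differ by about 0.3 percentage points (2.7% against 3.0%).
- A reader might extend the figures to marked laboratory abnormalities, which also get an EAIR. The Table of Events schedules no laboratory tests at the follow-up visit, so the figures apply to adverse events only.

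**Conclusion.** The mismatch is in the text and its direction is upward. For adverse events at the final analysis, the bound is about 10% to 12% in the Apremilast-exposure Period and about 2.7% in the Placebo-controlled Phase at 15% dropout. Both assume rare events, a tail hazard equal to the on-treatment hazard and uniform dropout; the first also assumes the extension dropout and early-escape ranges above. The inequality between phases holds only on the SAP 5.2 and 5.5 window.

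A reader might infer that long-term rates will therefore appear to rise with exposure. The documents do not support that as an expected result: front-loaded events pull the long-term EAIR down, and the size of the distortion depends on how many events start off drug. What is supported is a small definitional inconsistency in a descriptive statistic.

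One wording gap remains. For an event starting in the tail, SAP 9.6.1 does not say whether exposure ends at the last dose or at the event. The choice moves the inflation by at most about 0.5 percentage points.

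**What to change.** For adverse-event EAIRs only, use the same window in numerator and denominator, in one of two ways:

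- **Keep the 28-day tail and count its time.** For a subject without the event, time at risk runs from first dose to the earliest of last dose plus 28 days, phase stop date, data cutoff, last contact or death. For a subject with the event, it runs to the event's start date. The cap at last contact avoids crediting unobserved days to subjects lost to follow-up. The denominator should then be labeled time at risk.
- **Count only events starting up to the last dose, over treatment duration.** This keeps the stated interpretation per subject-year of exposure to the product. The EAIR numerator may then differ from the treatment-emergent incidence tables.

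Leave marked laboratory abnormalities on treatment duration. Reconcile the SAP 9.6.1 sentence on premature discontinuers with SAP 5.2 and 5.5, so that it is clear whether completers carry the tail.

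The cost is one derivation change. Adverse-event EAIRs become slightly lower and may not match the convention in earlier programme tables, which a footnote can state.

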#### 9.6.2 Adverse Events

The Medical Dictionary for Regulatory Activities (MedDRA) version 25.1 or later will be used to code all events categorized as adverse events to a system organ class and a preferred term with SOCs presented in the standard international order and PTs within SOCs will be presented in descending order of subject incidence.

The subject incidence of adverse events will be summarized for all treatment-emergent adverse events, drug-related treatment-emergent adverse events, severe adverse events, serious adverse events, adverse events leading to discontinuation of investigational product, fatal adverse events and adverse events of interest.

Protocol Number: 20200058

Date: 07 February 2023

Page 56 of 67

A subject data listing of all AEs (including TEAEs and non-TEAEs) will be provided.

An overall summary of the following AE categories will be provided:

- Any TEAE
- Any drug-related TEAE
- Any severe TEAE
- Any serious TEAE
- Any serious drug-related TEAE
- Any TEAE leading to drug interruption
- Any TEAE leading to drug withdrawal
- Any TEAE leading to death

Summarization of the following AE categories will be provided:

- Any TEAE (by SOC and PT, and by PT only)
- Common TEAE (subject incidence ≥ 5% by SOC and PT, and by PT only)
- Any serious TEAE (by SOC and PT)
- Any non-serious TEAE (by SOC and PT)
- Any drug-related TEAE (by SOC and PT)
- Any serious drug-related TEAE (by SOC and PT)
- TEAEs by maximum severity (by SOC and PT)
- Any TEAE leading to study drug withdrawal (by SOC and PT)
- Any TEAE leading to study drug interruption (by SOC and PT)
- Any TEAE leading to death (by SOC and PT), if applicable

If a subject reports multiple occurrences of a specific event within a specific analysis phase/period, the subject will be counted only once by the maximum severity (mild, moderate, severe, and, if needed, missing). If the severity is missing for one or more of the occurrences, the maximum severity of the remaining occurrences will be used. If the severity is missing for all occurrences, the subject will be counted only once in the "missing" category of severity.

Protocol Number: 20200058

Date: 07 February 2023

Page 57 of 67

The relationship of an AE to IP is recorded on the AE CRF page as "not suspected" and "suspected". Adverse events recorded as "suspected" or with missing relationship to IP will be assessed as drug-related.

Summaries about selected TEAEs will also be provided by onset day and the event duration.

New events of all TEAEs by exposure interval will be summarized for the Placebo-controlled Phase ( $\leq 1$ , > 1 to  $\leq 4$ , > 4 to  $\leq 8$ , > 8 to  $\leq 12$ , > 12 weeks) and the Apremilast-exposure Period ( $\leq 1$ , > 1 to  $\leq 4$ , > 4 to  $\leq 8$ , > 8 to  $\leq 12$ , > 12 to  $\leq 16$ , > 16 to  $\leq 28$ , > 28 to  $\leq 40$ , > 40 weeks). An event with a start date falling into an exposure interval is considered a new event for that interval. Each subject is counted once in the numerator of a subject incidence for each applicable specific TEAE in each exposure interval where an event started. The denominator of a subject incidence is the number of subjects with treatment duration exceeding the lower bound of the particular exposure interval.

All TEAEs will be summarized by age, sex, glucocorticosteroid use at baseline and prior/concomitant use of csDMARD. Subgroups of glucocorticosteroid use at baseline and prior/concomitant use of csDMARD will be based on the actual data, not by the data from IWRS.

If there are deaths, a listing will be provided.

#### 9.6.3 Adverse Events of Special Interest

AESIs include protocol defined diarrhea AEs, which refers to events with two or more watery or liquid stools in a day, will be captured on the tablet by ERT. Frequency of the individual diarrhea will be captured.

Frequencies (Daily, 5 - 6 days per week, 2 - 4 days per week, once every other week to once a week, once a month or less) of these events will be summarized.

The summaries will be generated for the Placebo-controlled Phase, and for the Apremilast-exposure Period.

#### 9.6.4 Laboratory Test Results

Summary statistics of observed values and changes from baseline in laboratory parameters will be provided by time points. For each hematology and chemistry analyte, frequency summaries of shifts from baseline to post-baseline time points and to the worst post-baseline value during each treatment phase will be provided. The low,

Protocol Number: 20200058 Date: 07 February 2023

normal, and high categories of laboratory values used in the shift will be based on the laboratory normal range.

Laboratory marked abnormalities will be summarized based on the criteria in marked abnormalities criteria (Appendix B). Subject incidence and EAIR for each abnormality will be calculated based on subjects with a baseline value and at least one post-baseline value for criteria requiring baseline or subjects with at least one post-baseline value for criteria not requiring baseline. A separate summary of laboratory marked abnormalities will also be presented by categories of subjects with normal values at baseline and subjects with abnormal values at baseline. To the purpose of these summaries, subjects with abnormal (normal) values at baseline are defined as those whose baseline value is low (not low) for criteria concerning low values and those whose baseline value is high (not high) for criteria concerning high values; both low and high are relative to the laboratory normal range. A subject data listing of laboratory marked abnormalities will be provided. In the listing, all recordings of a lab analyte will be displayed for the subject if that subject has one or more marked abnormalities for the test.

For comorbid conditions of interest or a subgroup of subjects, summary statistics of relevant laboratory parameters over time may be provided. Subject data listings of all laboratory data, including urinalysis, will be provided.

Clinical laboratory evaluations will be available from the central laboratory and include:

- Hematology: complete blood count (red blood cell [RBC] count, hemoglobin, hematocrit, white blood cell [WBC] count and differential, absolute WBC counts, platelet count).
- Serum chemistries: total protein, albumin, calcium, phosphorous, glucose, triglycerides, total cholesterol [TC], total bilirubin, alkaline phosphatase, aspartate aminotransferase [AST; serum glutamic-oxaloacetic transaminase, SGOT], alanine aminotransferase [ALT; serum glutamic-pyruvic transaminase, SGPT], sodium, potassium, chloride, bicarbonate [carbon dioxide, CO2], blood urea nitrogen, creatinine, creatinine clearance [estimated by the Cockcroft–Gault equation], lactate dehydrogenase [LDH], magnesium
- Dipstick urinalysis: specific gravity, pH, glucose, ketones, protein, blood, bilirubin, leukocyte esterase, nitrite, and urobilinogen. Dipstick urinalysis will be performed by the central laboratory; if the dipstick urinalysis is abnormal then a microscopic urinalysis (epithelial cells, RBC, WBC, and casts) will be performed.

Page 58 of 67

Protocol Number: 20200058 Date: 07 February 2023

A subject listing will be provided for all available pregnancy test results.

